### Benefits

- Knowledge gained. Although the study may not benefit participants directly, this study could provide important information on how to address issues of cancer misinformation. Because risks to participants in this study are minor, the risks are reasonable in relation to the expected benefits.
- Financial compensation. Participants will receive \$75 for playing the game, participating in a post-game brief interview, and completing baseline and post-intervention surveys.

## 3.0 OVERVIEW OF STUDY

### 3.1 Study Objectives

The overarching goal of this research study is to pilot test an escape room intervention for cancer nutrition misinformation designed to reduce vulnerability to believing cancer nutrition misinformation among breast cancer patients. The main aim (Aim 1) is to determine the potential feasibility, acceptability, and usability of the intervention. The secondary aim (Aim 2) is exploratory in nature and designed to determine if there are potential changes in pre/post outcome measures (increasing awareness about types of online misinformation, concern about misinformation, and confidence in the ability to identify misinformation). The results of this pilot study will provide necessary preliminary data to apply for an NIH R01 level application to conduct a full randomized controlled trial (RCT) of the escape room game as a potential intervention to increase resistance to cancer nutrition misinformation.

### 3.2 Specific Aims

#### Aim 1

To evaluate the feasibility (1a), acceptability (1b), and usability (1c) of the escape room game intervention among breast cancer patients in active treatment.

Hypothesis 1a: For feasibility,  $\geq 50\%$  of screened eligible patients will enroll in the study.

Hypothesis 1b: For acceptability,  $\geq 70\%$  of patients will rate the intervention as satisfactory (e.g., a "7" or higher on a 10-point Likert scale) on a 10-point Likert-scale item assessing how satisfied they are with the intervention and will recommend this game to others.

Hypothesis 1c: For usability,  $\geq 70\%$  of patients will have a System Usability Score (SUS) of  $\geq 68$ .

**Exploratory Aim 2**

To test preliminary efficacy of the escape room game intervention for increasing awareness about types of online misinformation, concern about misinformation, and confidence in the ability to identify misinformation as well as decreasing cancer nutrition misinformation beliefs.

**Hypothesis 2:** Cancer patients will report increases in awareness about types of online misinformation, concern about misinformation, and confidence in the ability to identify misinformation and reductions in believing cancer nutrition misinformation from pre- to post-intervention.

**3.3 Study Population**

The study includes patients with a current diagnosis of breast cancer and/or are receiving treatment for breast cancer.

**3.4 Study Design****Intervention Description**

[figure not shown]
The intervention is an escape room game designed to teach participants how to discern whether cancer nutrition information is accurate or may potentially be misinformation. The content of the game focuses on common tactics used to spread misinformation such as cherry-picking study data, using questionable “expert” influencers, overgeneralization, and misleading headlines. The game is designed to be played in groups of approximately 5, in which players work together to solve a series of puzzles that teaches them about the potential risks of misinformation online. In the present study, the intervention will follow a fictional company (“ZenFusion Wellness”) that is trying to sell its nutritional product (The “Evergreen Diet”) in order to make profits. Throughout the game, players are immersed in the narrative while solving puzzles to learn key themes such as the need to talk to their doctors and look for scientific studies and FDA approvals as well as avoid fads and trends, miracle cures, anecdotal evidence, and targeted and clickbait ads. For example, in one puzzle, participants are asked to “decode” the sensationalist ad headlines and use the codebook to find a password. The headlines are designed to mimic programmatic ads often seen at the bottom of websites with text such as “This one simple trick will help you heal naturally” and “This woman conquered breast cancer through diet alone.” **Figure 1** provides a screenshot of the puzzle. Below, we also outline all five puzzles included in the game.

**Figure 1. Escape Room Puzzle**

[figure not shown]
Your supervisor says that your competitor's ad headlines always grab people's attention and they need you to decode a corrupted file with examples of their ads.

Can you figure out what the original ads were saying, so your company can adopt this language too?

You may use the text boxes below each headline and along the side for note-taking.

**Puzzle 1: Distrust doctors?** Find an  $\{ = < % > \$ \{ < * \sim \%$ .   
   

**Puzzle 2: This one simple trick will help you heal**  $\$ \{ < _ > \{ = \backslash$ .   
   

**Puzzle 3: This woman ^ + \$ } - % > % & breast cancer through diet alone**  $\# _ ] \% > / + + \& \#$  are the key to beating cancer.   
   

**Codebook:**

{	
=	
<	
%	
>	
\$	
*	
~	
-	
\	
^	
,	
+	
}	
&	
@	
#	
]	
/	

- **Puzzle 1:** This puzzle is a visual representation of the spread of strong emotions via social media. Players are shown an unfinished grid puzzle with smiley face emojis depicting different emotions. Players are asked to rearrange pieces of the puzzle, and after doing so, an image will be revealed that gives a clue to the secret password. When the secret password is entered correctly, the game continues.
- **Puzzle 2:** This puzzle is primarily text-based and reflects tactics of misleading advertising. It provides several partially finished headlines related to nutrition. Players are asked to work together to decode the letters / words (e.g., “The Cancer-Free Diet: Eat your way to >%!\*##\*+\$” when solved becomes “The Cancer-Free Diet: Eat your way to **remission**”). When solved correctly, players will be able to decode the secret password.
- **Puzzle 3:** This puzzle is in two parts and reflects tactics used to cherry pick data and only present successful outcomes. Part One is a matching game, where players flip over cards and make pairs (each image has a food and a person). Once matched successfully, players begin Part Two, where they match the foods with people that were linked in Part One. This reveals a secret password.
- **Puzzle 4:** This is a Hashi bridge puzzle that requires players to connect nodes in a network. Each player works on their own individual puzzle, connecting dots with one or two lines. Correctly solved puzzles will visually form a letter—all four letters revealed spell out the secret password.
- **Puzzle 5:** This puzzle is a maze and represents individual patient health journeys and how to navigate through uncertainty. Each player solves their own maze by clicking on tiles that will form the correct path associated with images that correspond to parts of the care journey that should be adopted (e.g., scientific studies, consultations with medical professionals) rather than those that should be avoided (e.g., fads and trends, miracle cures). Once all players solve their maze, the secret password is revealed.
- **Final Task:** Before the game ends, players are asked to select an option to finish the story. All options are acceptable and lead to winning the game. Players’ discussion of options will preface the next stage of the intervention, which is the hosted debrief.

The game is designed to be played only once by players. It is a collaborative group appropriate for 3-5 players to play together. The length of the game is approximately 30-45 minutes depending on how quickly participants solve the puzzles. The game will be played online via a video-calling platform (i.e. Zoom).

At the end of the game, players are expected to be more aware of possible nutrition misinformation that may be online and to be wiser consumers of online information.

Eight groups of approximately 5 participants (n=40 total) will be recruited and grouped together. Participants will be provided a baseline survey prior to their attendance at the session. Participants will play the misinformation escape room game together with the group and take part in a debrief with a member of the research team immediately after completing the game. Finally, participants will be provided with a post-game survey to complete after the game and debrief session.

### 3.5 Name of Sponsor/Funding Source

Fred Hutchinson Cancer Center, Cancer Consortium Grant (NIH/NCI)

## 4.0 PARTICIPANT ELIGIBILITY

### 4.1 Inclusion Criteria (Patients)

#### Inclusion Criteria:

- 1) Age 18 years of age or older.
- 2) English speaking.
- 3) Able to provide informed consent.
- 4) Have access to a computer (desktop or laptop).
- 5) Have been previously diagnosed with breast cancer (Stages I-III) and currently in active treatment for breast cancer.

**Exclusion Criteria:**

[figure not shown]
- 1) No other exclusion criteria.

**5.0 PARTICIPANT REGISTRATION**

When potential study participants are identified, Fred Hutch research staff will enter their information into the secure REDCap database, as well as into OnCore CTMS. A complete, written or electronically signed, study consent and HIPAA authorization form are required for registration.

**STUDY SCHEMA**

Review list of breast cancer patients at Fred Hutch and University of Washington for potentially eligible participants

**6.0 STUDY PROCEDURES AND INTERVENTION****6.1 Recruitment strategies**

- 1) Physician support. Prior to initiating recruitment, physicians seeing breast cancer patients at Fred Hutch will be introduced to the study and it will be requested that their eligible patients be approached for study participation.
- 2) EPIC reports. We will use EPIC reports to identify patients who meet eligibility criteria. The reports will include the patient's name, age, gender identity, and next appointment details. Once patients are identified, study staff will approach patients in person or contact patients via phone to discuss the study and screen for eligibility.
- 3) Direct referrals and patient lists from breast cancer clinics. The breast cancer patient lists will be queried to identify potential participants and clinicians will also provide direct referrals. Clinicians can send study staff the names and MRNs of potential patients and/or provide study staff contact information to interested patients. Once patients are identified, study staff will approach patients in person or contact patients via phone to discuss the study and screen for eligibility.
- 4) Support groups. Study staff will communicate about the study through online patient support groups for breast cancer patients. Study staff will send e-mail messages to support groups. Potential participants will provide the University of Washington team with the following pieces of information: age, breast cancer stage, number of months since diagnosis, demographics.

## 6.2 Estimated Accrual

Our goal is to consent 40 study participants total (8 groups of n=5). Based on clinic volume and patient flow, we estimate that we can approach and consent n=40 patients within 6 months. On average, in each year of 2020 and 2021, approximately 1,659 new breast cancer patients were diagnosed and treated at Fred Hutch (formerly SCCA), with 1,492 being stage 0-III breast cancer patients. Thus, our proposed recruitment goal is achievable. If a patient drops out prior to the intervention, they will be replaced to reach a final n of =40.

## 6.3 Consent and Data Collection

If a participant is interested and eligible, study staff will confirm email address and cell phone number. Participants will determine mode of sending communication, either via phone or email.

**Table 1** provides information on data collected in this study survey. Please note that some measures map directly on to Study Aims 1 and 2 and other variables are exploratory in nature, as we anticipate the game to influence these variables as well.

**Table 1. Survey measures to be collected**

	Screening	Baseline	Post -completion of intervention (+ 1 week)
Demographics & clinical characteristics	X	X	
Disease status and treatment		X	X
Behaviors done based on information consumed online (a 6-item background checklist such as "taken over-the-counter medicine")		X	
Aim 1			
Feasibility			X
Acceptability			X
Usability			X
Aim 2			
Types of online information (as measured by 6-item checklist about sources of nutrition information utilized)		X	
Concern about misinformation and confidence in identifying misinformation			X
Cancer nutrition misinformation beliefs (as measured by cancer nutrition beliefs)		X	X
Additional exploratory variables			
Trust and information-seeking		X	X
Vulnerability to misinformation		X	X
Healthy skepticism		X	X
Confidence in and motivation to share information with a medical professional		X	X
Awareness of misinformation		X	X
Exit/debrief questions and interview			
Game enjoyment/recommendation to others			X
Qualitative exit interview			X

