## PROTOCOL SYNOPSIS

Protocol Title	Escape Room: A gamified approach to learning about cancer nutrition information
Protocol Number	
Protocol Sponsor	Fred Hutchinson Cancer Center
Trial Phase	Early Phase/Phase 1
Trial Type	Single arm, open trial
	Aim 1 To evaluate the feasibility, acceptability, and usability of the escape room game intervention among breast cancer patients in active treatment.
Study Objectives	Exploratory Aim 2 To test preliminary efficacy of the escape room game intervention for increasing awareness about types of online misinformation, concern about misinformation, and confidence in the ability to identify misinformation as well as decreasing cancer nutrition misinformation beliefs.
Study Design	Feasibility study (Aims 1 and 2)
Population	Patients with a current diagnosis of breast cancer (Stages I-III) and in active treatment for breast cancer.
Primary Endpoints	Study design and intervention feasibility, acceptability, usability, and potential efficacy of an escape room game will be measured by assessing accrual rate, satisfaction, and usability of the escape room game.
Secondary Endpoints	Awareness and concern about cancer nutrition misinformation and beliefs about cancer nutrition.
Type of Control	N/A (single arm, open trial)
Treatment Group	Escape room game
Treatment Schedule	Intervention (Escape Room Game): 
 
- Pre-game baseline survey
 
- Play the misinformation escape room game intervention in groups of approximately 5 and completed debrief exit interview
 
- Post-game survey
 

Number of participants	N=40 (n=5 breast cancer patients per group)
Estimated duration of study (per participant)	4 weeks
Duration of participation (per participant)	90 minutes

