## 2.0 INTRODUCTION TO THE PROTOCOL

### 2.1 Introduction

The described study will be conducted in compliance with all applicable IRB requirements and associated Federal regulations.

The overarching goal of this research study is to pilot test an escape room intervention for cancer nutrition misinformation designed to reduce vulnerability to believing cancer nutrition misinformation among breast cancer patients. The results of this pilot study will provide necessary preliminary data to apply for an NIH R01 level application to conduct a full randomized controlled trial (RCT) of the escape room game as a potential intervention to increase resistance to cancer nutrition misinformation.

[name] (Co-I) and [name] (Co-I) at the University of Washington (UW), along with collaborator [name] (Puzzle Break), previously developed an online misinformation escape room as an interactive learning experience designed to focus on the psychological dimensions of misinformation. Escape rooms are live action-adventure games where teams work cooperatively to solve a series of puzzles. Initial results were encouraging, indicating the game successfully increased awareness of misinformation and confidence in identifying it. Based on this experience, the UW research team and [name] (PI) at Fred Hutch partnered to develop an escape room for cancer nutrition misinformation. This project builds off [name] key strengths as a cancer communication researcher and builds on a novel and relevant area of public health – combating cancer misinformation. Expertise from oncologists and cancer nutrition experts about the types of misinformation they encounter in their work with patients was also incorporated into developing the escape room content.

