## Data Collection

Eligible participants will undergo in person or remote assessments that will include in person, over the phone, video conferencing, and/or web-based data collection.

Data collection will include completion of a written or electronic eConsent form via a secure HIPPA-compliant REDCap survey and the following assessments: (1) Questionnaires assessing demographics, medical history, clinical characteristics (pre- and post-intervention); (2) *Feasibility* will be assessed by rates of accrual to the study; (3) *Acceptability* will be assessed using two Likert-type scales to assess satisfaction (1 = not at all satisfied, 10 = very satisfied) and likelihood to recommend the game to someone else (1 = not at all likely, 5 = very likely) (post-intervention); (4) *Usability* will be assessed with the System Usability Scale (SUS) (post-intervention only), which is a 10-item scale, scored on a 5-point Likert scale (1 = strongly disagree, 5 = strongly agree) (post-intervention); (5) *sources of nutrition information utilized* (6-item checklist) (baseline), (6) *behaviors done based on information consumed online* (6-item checklist) (baseline); (7) *trust and information-seeking* (5-item scale scored on a 7-point Likert scale; 1 = strongly disagree, 7 = strongly agree) (baseline and post-intervention); (8) *vulnerability to misinformation* (3-item scale scored on a 7-point Likert scale; 1 = strongly disagree, 7 = strongly agree) (baseline and post-intervention); (9) *healthy skepticism* (6-item scale scored on a 7-point Likert scale; 1 = strongly disagree, 7 = strongly agree) (baseline and post-intervention); (10) *confidence in sharing and motivation to share information with a medical professional* (2 items from the "Confidence Sharing Information with a Medical Professional" scale scored on a 7-point Likert scale; 1 = not at all confident; 7 = very confident and 2 adapted items to measure degree of motivation; 1 = not at all motivated, 7 = very motivated) (baseline and post-intervention); (11) *Awareness of misinformation* (baseline and post-intervention), (12) *Concern about misinformation and confidence in identifying misinformation* (baseline and post-intervention), (13) *Cancer nutrition information beliefs* (baseline and post-intervention), and (14) brief semi-structured feedback exit interview (post-intervention only).

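### Awareness of misinformation is a secondary endpoint and the first pre/post outcome of Hypothesis 2, but the Aim 2 measure lists omit it, file its two-time-point scale as exploratory, and 13.2 names no analysis for it

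*Combined protocol and SAP*

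**What the plan says.** The synopsis gives the secondary endpoints as "Awareness and concern about cancer nutrition misinformation and beliefs about cancer nutrition". Section 3.1 describes Aim 2 as "designed to determine if there are potential changes in pre/post outcome measures (increasing awareness about types of online misinformation", followed by concern and confidence. Hypothesis 2 in 3.2 begins "Cancer patients will report increases in awareness about types of online misinformation" and goes on to concern, confidence and lower belief in misinformation, all from pre- to post-intervention.

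Section 6.3 introduces Table 1 by saying that "some measures map directly on to Study Aims 1 and 2 and other variables are exploratory in nature". The first Aim 2 row of the table is "Types of online information (as measured by 6-item checklist about sources of nutrition information utilized", marked at baseline only. The Aim 2 list in 7.1 opens with the same checklist and describes it as the resources that participants or their families used over the previous 3 months. Neither Aim 2 list has an entry for awareness.

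The awareness scale appears further down. Table 1 puts it among the additional exploratory variables, marked at both baseline and post-intervention. Section 7.1 puts it under exploratory outcomes, as a 5-item scale of how aware users become of misinformation types and tactics. Item 11 of the Data Collection text in 6.3 confirms both time points.

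Section 13.2 plans repeated measures ANOVAs on the misinformation belief scales, to assess change in those beliefs. It names no other quantitative pre/post outcome.

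**The concern.** An outcome that the hypothesis expects to change needs a measure taken at both time points and an analysis assigned to it. For awareness, the sections that assign measures and analyses do not match the sections that state the aims. An analyst who took the Aim 2 lists and 13.2 literally would report Aim 2 with a baseline source checklist, no awareness result and no planned awareness comparison.

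The pilot is meant to supply preliminary data for an application to run a full randomized trial (2.1 and 3.1). Awareness is also one of the two results that 2.1 cites from the team's earlier escape room, "indicating the game successfully increased awareness of misinformation and confidence in identifying it". If the documents do not settle beforehand which instrument carries this outcome, the choice is left until results are in hand.

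**Working it through.** The plan gives no figure to reproduce, so the check sets its sections side by side.

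**Outcomes against measures and analysis.** The four outcomes are those of Hypothesis 2.

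| Outcome | Measure in Aim 2 lists (Table 1, 7.1) | Timing in Table 1 | Timing in 6.3 Data Collection | Named in 13.2 |
|---|---|---|---|---|
| Awareness | None; the scale is filed as exploratory | Baseline and post | Baseline and post (item 11) | No |
| Concern | Yes, scale shared with confidence | Post only | Baseline and post (item 12) | No |
| Confidence | Yes, scale shared with concern | Post only | Baseline and post (item 12) | No |
| Beliefs | Yes | Baseline and post | Baseline and post (item 13) | Yes |

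**Counts.**
- Outcomes with a measure of the right construct in the Aim 2 lists: 3 of 4. Awareness is the one without.
- Outcomes whose Aim 2 row in Table 1 is marked at both time points: 1 of 4 (beliefs). With the Data Collection timing instead, it is 3 of 4. Awareness is missing on either count.
- Outcomes with a pre/post analysis named in 13.2: 1 of 4 (beliefs), so 4 − 1 = 3 have none. Section 3.1 lists three pre/post outcomes (awareness, concern, confidence), and 13.2 names 0 of those 3.

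**Can the checklist serve as the awareness measure?** There are two independent reasons why not.
- Timing: Table 1 and item 5 of the Data Collection text both place it at baseline only. With one time point, post minus pre cannot be formed.
- Content: it records which sources were used. Repeating it after the game would show a change in sources, not in awareness.

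**Does the awareness scale fit?** Yes. Its description in 7.1 matches the construct in Hypothesis 2, and it has two time points in both Table 1 and the Data Collection text.

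**Does the checklist occupy the place of awareness?** This is an inference. Hypothesis 2 runs awareness, concern, confidence, beliefs. Data Collection items 11 to 13 run awareness, concern with confidence, beliefs. The Aim 2 rows of Table 1 run source checklist, concern with confidence, beliefs. The checklist therefore sits in the first position, under a label close to the hypothesis wording but with *information* where the hypothesis has *misinformation*. The Data Collection text also lists it directly before the online-behaviors checklist, which Table 1 treats as background: "Behaviors done based on information consumed online (a 6-item background checklist".

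**How firm is the reading of 13.2?** The plural *scales* leaves some room, because 7.1 defines only one belief instrument. But the stated purpose is change in beliefs, and a scale that runs from not aware to fully aware is not naturally a belief scale.

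**The case against.** The strongest reply is that little turns on the label. Aim 2 is itself exploratory, no alpha or hierarchy separates its measures from the additional exploratory variables, and 6.3 says the game is expected to influence those variables as well. Change in awareness is thus of interest under either heading, the scale is specified, and its timing is consistent. All of this stands, and it limits the consequence. It does not remove the contradiction: 6.3 gives the grouping a meaning, and the synopsis names awareness as an endpoint.

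A second reply is that no section calls the checklist an outcome or a measure of awareness. Table 1 is a list of survey measures, and the checklist could be a descriptive Aim 2 variable. This also stands. A reader might infer that the protocol has designated the checklist as its awareness outcome, but the documents do not say so. The point needs only the weaker fact that the Aim 2 lists have no awareness measure.

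A third reply is that awareness is not alone. Table 1 marks concern and confidence post only, and 13.2 does not name them either. That is correct. A reader might infer that awareness is the only Hypothesis 2 outcome the plan neglects; in fact only its absence from the Aim 2 lists is peculiar to it, and the gap in 13.2 covers three outcomes.

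**Conclusion.** The point holds as a fault in outcome mapping and in the named analysis. Awareness is a secondary endpoint and a Hypothesis 2 outcome with no measure in the Aim 2 lists. On the natural reading of 13.2, 3 of the 4 Hypothesis 2 outcomes have no named pre/post analysis.

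The absence of awareness from the Aim 2 lists is plain on the page. The 13.2 count assumes that the belief scales there are the belief instrument of 7.1; a broader reading of the plural would shrink that gap but would leave the mapping fault.

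A reader might go further and infer that awareness will not be measured, or that Hypothesis 2 cannot be examined for it. The documents do not support that: the scale is planned at both time points, and a careful analyst could recover the intent from 6.3 and 7.1. Nor are error rates or sample size affected, because Aim 2 has no decision rule. The consequence is confined to which results are reported for Hypothesis 2. That merits correction, given the pilot's role in the next application.

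**What to change.** In Table 1 and 7.1, list the existing 5-item awareness scale as the Aim 2 awareness outcome, and move the source checklist to background, next to the online-behaviors checklist.

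In 13.2, apply the repeated measures pre/post analysis already stated there to every Hypothesis 2 outcome with baseline and post data. That means awareness and beliefs now, and concern and confidence once Table 1 and item 12 of the Data Collection text are reconciled on their timing, which is a separate point. Naming only awareness and beliefs would leave 2 of the 4 outcomes without an analysis. Report all of these as exploratory changes.

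The cost is protocol wording (two table rows and two bullets regrouped, one sentence in 13.2 extended) and a few extra model fits. For awareness, no new data, visits or patients are needed.

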## 7.0 PARTICIPANT EVALUATION

### 7.1 Study Questionnaires and Assessments

- **Background information**
  - *Demographic and disease characteristics* will include age, gender, race/ethnicity, education level, marital and parental status, income, cancer type, date of diagnosis, and cancer stage.
  - *Behaviors done based on information consumed online* will be assessed with a 6-item checklist asking which behaviors participants have done because of something they saw on the Internet (e.g., "Taken an over-the-counter medicine or supplements, for example, vitamins, minerals, or nutritional supplements").
- **Aim 1:**
  - *Feasibility* will be assessed by rates of accrual and completion of game sessions.
  - *Acceptability* will be assessed using two Likert-type scales to assess satisfaction (1 = not at all satisfied, 10 = very satisfied) and likelihood to recommend the game to someone else (1 = not at all likely, 5 = very likely).
  - *Usability* will be assessed using the System Usability Scale (SUS). The SUS is a reliable, 10-item measure 10-item scale, scored on a 5-point Likert scale (1=strongly disagree; 5=strongly agree), with previously reported excellent internal reliability (Cronbach's  $\alpha = 0.91$ ).
- **Aim 2:**

- *Types of online information* (e.g., *sources of nutrition information utilized*) will be assessed using a 6-item checklist that asks which resources participants or their family members have used to find nutrition information in the past 3 months (i.e., a self-care/health and wellness book, a telephone advice service, a booklet/flyer shared by a health professional, Internet forums, Internet search, social media).
- *Concern about misinformation and confidence in identifying misinformation* will be measured using our 4-item scale in which patients indicate degree to which they agree with statements (e.g., “I feel more confident in my ability to identify misinformation”; 1= strongly disagree, 5 = strongly agree).
- *Cancer nutrition information beliefs* will be measured using a 15-item checklist of common cancer nutrition misinformation and credible nutrition advice. Participants rate the items on a 5-point Likert-scale (1= definitely false, 5 = definitely true).
- **Exploratory outcomes:**

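### Table 1 schedules the concern and confidence scale after the game only, although Section 6.3 item (12) and Hypothesis 2 require a baseline

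*Combined protocol and SAP*

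**What the plan says.** Section 6.3 introduces Table 1 with the statement that it "provides information on data collected in this study survey". Under Aim 2, the row "Concern about misinformation and confidence in identifying misinformation" is marked once, in the post-completion column. Its screening and baseline cells are empty.

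The Data Collection text in the same section lists 14 assessments with their timing. Item (12) reads "Concern about misinformation and confidence in identifying misinformation* (baseline and post-intervention".

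The objectives depend on a baseline. Section 3.1 describes Aim 2 as looking for "changes in pre/post outcome measures (increasing awareness about types of online misinformation, concern about misinformation, and confidence in the ability to identify misinformation". Hypothesis 2 in Section 3.2 predicts increases in awareness, concern and "confidence in the ability to identify misinformation and reductions in believing cancer nutrition misinformation from pre- to post-intervention". The synopsis also lists concern among the secondary endpoints.

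Section 7.1 describes a four-item agreement scale, gives no timing for it, and shows one item: "I feel more confident in my ability to identify misinformation". Section 13.2 specifies repeated measures ANOVA for the belief scales and names no other pre/post outcome.

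**The concern.** The study has one arm, so the change from before to after the game is the only contrast available for Aim 2. An outcome measured only afterwards has nothing to be compared with.

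Staff building the REDCap forms could reasonably work from Table 1, and the example item would not alert them, since it reads naturally as a question asked after the game. A baseline missed in this way is lost for good. Section 3.4 says "Participants will be provided a baseline survey prior to their attendance at the session" and "The game is designed to be played only once by players". The pilot is meant to supply preliminary data for an application to run a randomised trial, and it would then have no change estimate for two of the outcomes it set out to examine.

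**Working it through.** There is no planned figure to reproduce; the check compares schedules.

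**Step 1. Is the conflict isolated?** I compared the timing of all 14 items in the Data Collection list with Table 1.

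| Data Collection item | Text | Table 1 | Result |
|---|---|---|---|
| (1) background questionnaire | baseline and post | split over two rows: screening and baseline; baseline and post | partial match |
| (2) feasibility | no time given | post | not comparable |
| (3), (4), (14) | post | post | agree |
| (5), (6) | baseline | baseline | agree |
| (7) to (11), (13) | baseline and post | baseline and post | agree |
| (12) concern and confidence | baseline and post | post only | conflict |

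The totals are 3 + 2 + 6 = 11 in agreement, 1 partial, 1 not stated and 1 in outright conflict. Seven scales, items (7) to (13), are labelled as baseline and post in the text. Six of them carry both marks in Table 1, and only item (12) does not. The text also separates baseline-only and post-only measures from these, so the label on item (12) is not loose general wording.

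**Step 2. What does Hypothesis 2 lose?**

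| Hypothesis 2 outcome | Both time points under Table 1 | Both time points under the text |
|---|---|---|
| Awareness | yes | yes, item (11) |
| Concern | no baseline | yes, item (12) |
| Confidence | no baseline | yes, item (12) |
| Misinformation beliefs | yes | yes, item (13) |

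Following Table 1, 2 of 4 outcomes have no baseline; following the text, 0 of 4. The same cell carries 2 of the 3 outcomes named in Section 3.1 and 1 of the 3 synopsis secondary endpoints (concern). Following Table 1, 0 of 40 participants would have a change score on either outcome.

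**Step 3. Would a baseline mark be enough?** Not for the item shown. Asking someone before the game whether they feel more confident measures perceived change from an unstated reference point, not a current level. This is established for 1 of the 4 items; the other three are not given. By contrast, the awareness scale in Section 7.1 is anchored on how aware the respondent is, which works at both times.

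**Step 4. Is an analysis named?** Section 13.2 clearly covers 1 of the 4 outcomes, beliefs. Its plural might be meant more widely, but the stated purpose is change in beliefs. Awareness, concern and confidence are not named.

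**Step 5. Burden of the change.** Items already scheduled at baseline, from the stated counts: behaviours 6 + sources 6 + beliefs 15 + trust 5 + vulnerability 3 + skepticism 6 + sharing with a professional 4 + awareness 5 = 50. The total is 49 if Section 7.1's count of three sharing items is used. Demographic and clinical questions are excluded. Four more items add 4/50 = 8.0% or 4/49 = 8.2%.

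**The case against.** The strongest counter-argument is that Table 1 may be right and item (12) the slip. The only item shown suits a single administration after the game, and the Data Collection list is not a complete master list, since it omits the game enjoyment row of Table 1. This has some force and is why the wording must be settled together with the timing. It does not outweigh Section 3.1, Hypothesis 2 and item (12), all of which call for a baseline.

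A second argument is that something would survive without a baseline. A perceived-change item gives weak evidence of a reported increase, and the vulnerability and healthy skepticism scales, both taken twice, touch on confidence. That is fair as far as it goes. Neither is the designated measure, neither visibly covers concern, and Section 3.1 asks for pre/post change.

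A third is that the count of two in four assumes awareness is measured by the five-item scale listed as exploratory. The Aim 2 block of Table 1 instead holds a baseline-only checklist of information sources. The assumption is reasonable, because Section 7.1 says the five-item scale covers types of misinformation. If the checklist were the intended measure, awareness would lack a post-game value and three of four outcomes would have no pre/post pair, which is worse.

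Finally, Aim 2 is exploratory and the loss is conditional on the survey following the table. Both points are true and limit the severity.

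**Conclusion.** The contradiction is real and sits in the current text. One table cell decides whether two of the four Hypothesis 2 outcomes can be examined as pre-to-post changes. It should be corrected, but it does not threaten the main purpose of the study: 0 of the 3 Aim 1 hypotheses are affected, and awareness and beliefs have both time points in table and text.

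This rests on three assumptions:

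- The survey is built from Table 1. The forms themselves are not in the documents.
- The single mark is what the table really shows. A mark lost in text conversion cannot be wholly excluded and is worth a glance at the PDF, but neighbouring two-mark rows are intact and this row matches the post-only rows.
- Awareness is measured by the five-item scale.

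Confidence in the finding is high.

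**What to change.** 1. Add a baseline mark to the concern and confidence row of Table 1, so that it agrees with item (12), Section 3.1 and Hypothesis 2.
2. Before the baseline survey is fielded, read all four items. Reword any that presuppose change so that they ask about the respondent's present state, in identical words at both times. An individual item may instead be kept in its change wording, given after the game only and reported descriptively as perceived change. This option should not be used for the whole scale: concern and confidence each need at least one item asked in the same form at both times, or the added baseline serves no purpose.
3. In Section 13.2, name awareness, concern and confidence with the belief scale as the pre/post outcomes of Hypothesis 2.

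The cost is one table cell, a check of four items and one sentence. Participants answer four more baseline items than Table 1 implies, about 8% more, and any reworded item loses some comparability with the team's existing scale. The documents do not show whether the survey is already in use. If it is and the baseline was omitted, the report should say so and present these two outcomes as post-game descriptions for the participants affected.
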